## CONFIDENTIAL PROTOCOL

A Randomized, Double-Blind, Placebo-Controlled, Parallel-Design, Multiple-Site Clinical Study to Evaluate the Efficacy and Safety of Desoximetasone Topical Spray, 0.15% (Taro Pharmaceuticals, U.S.A., Inc.) in Patients with Mild to Moderate Plaque Psoriasis

---

Patients will be advised not to cover the skin being treated with bandages, dressings or wraps that will occlude the treatment area.

Patients will be questioned about all concomitant prescription and OTC medication use at each study visit. All concomitant medications will be recorded in the patient's study chart. Any patient who violates any of the listed restrictions may be dropped from continued participation in the study by the Investigator.

### 9.3.4 Removal of Patients from the Study

Patients will be advised that they are free to withdraw from the study at any time for any reason, or, if necessary, the Investigator may withdraw a patient from the study to protect the health of that patient. A patient may also be withdrawn for not complying with study procedures. The clinical report will include all reasons for early withdrawals.

Reasons for removal may include the following:

- Worsening signs/symptoms.
- Development of an intercurrent condition or complication that could affect the safety of the patient or the validity of evaluation of the patient's clinical state to an extent considered significant by the Investigator.
- Non-compliance with protocol.
- Signs and symptoms of possible hypothalamus-pituitary axis (HPA) axis suppression.
- Pregnancy.

Patients who withdraw or are removed from the study will not be replaced.

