### 9.3.5 Early Terminations

If a patient terminates from the study early, all efforts will be made to complete Visit 4 study procedures. In case of early termination the Investigator shall fully document the reason for early termination.

Patients who discontinue early or who significantly deviate from the protocol will be included in the intent-to-treat (ITT) population with LOCF.

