### **9.5.4 Visit 4 (Day 28 ± 2): End of Treatment**

1. **Vital Signs:** The patient's vital signs will be recorded (pulse, blood pressure, temperature and respiration rate).
2. **Dermatological Assessment:** Clinical signs and symptoms of psoriasis will be evaluated by the Investigator based on the following:
  - % BSA assessment (Appendix A)
  - IGA Score (Appendix C)
  - TLSS Score (Appendix B)
  - PASI Score (Appendix D)
  - Application Site Reactions (Appendix E)
3. **Pregnancy Test:** A pregnancy test will be required of all female patients of childbearing potential at the last study visit.

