### **9.6.7 Pregnancy Test**

All females of childbearing potential will have a urine pregnancy test performed at Visits 1 and 4. The test must be negative at Visit 1 for the patient to be eligible for inclusion in the study. If the patient is female and not considered of childbearing potential, then the reason must be documented in the patient's source documents.

Any patient who becomes pregnant during the study should be discontinued and end of treatment procedures (Visit 4) completed. The outcome of the pregnancy should be followed by the Investigator to the conclusion of the pregnancy.

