### **9.6.11 Dosing Compliance**

Dosing compliance will be checked by site staff at Visits 2, 3 and 4 by reviewing patient diary entries. Patients will be considered compliant with dosing if they administer 75%-125% of the required number of doses, and did not miss more than 3 consecutive days of dosing.

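### Sections 9.3.3 and 9.3.4 let a patient be removed from the study, not only from study drug, for non-compliance or a restriction breach, so an exit, Day 7 or Day 14 score can stand in for an obtainable Day 28 score

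*Protocol*

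**What the plan says.** Two protocol rules allow removal for conduct reasons. Section 9.3.4, on removal from the study, states: "A patient may also be withdrawn for not complying with study procedures". It also lists protocol non-compliance among the reasons for removal. Section 9.3.3 states: "Any patient who violates any of the listed restrictions may be dropped from continued participation in the study by the Investigator". Neither rule distinguishes stopping study drug from stopping assessment. The restrictions in 9.3.3 range from other psoriasis treatments to an emollient on the treated area or a non-sedating antihistamine.

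Breaches come to light at visits. Section 9.6.11: "Dosing compliance will be checked by site staff at Visits 2, 3 and 4 by reviewing patient diary entries". Section 9.3.3: "Patients will be questioned about all concomitant prescription and OTC medication use at each study visit".

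For those who leave, section 9.3.5 says: "If a patient terminates from the study early, all efforts will be made to complete Visit 4 study procedures". It gives no date. Section 9.5.4 is headed "Visit 4 (Day 28 ± 2): End of Treatment", which points to Day 28. Section 9.6.7, however, attaches the same procedures to discontinuation: "Any patient who becomes pregnant during the study should be discontinued and end of treatment procedures (Visit 4) completed". Section 11.2.4 has the Visit 4 case report form completed for early terminators.

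On analysis, section 9.3.5 says: "Patients who discontinue early or who significantly deviate from the protocol will be included in the intent-to-treat (ITT) population with LOCF". Section 10.3.1 puts all randomized patients in the ITT population, with LOCF for early discontinuation for any reason. Section 10.6 makes that the primary analysis. Section 10.5 defines both co-primary endpoints at Day 28 ± 2.

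**The concern.** A patient who missed doses or used an emollient has no safety reason to leave and could usually be scored at Day 28. If that patient is removed at Visit 2 or 3, the Day 28 score is never taken, and no later analysis plan can recover it. The ITT analysis then uses an earlier score for an endpoint defined at Day 28 ± 2. If the exit assessment goes on the Visit 4 form, the earlier score may also carry the Day 28 label.

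Removal brings no analytic gain. The per-protocol population (10.3.2) already excludes dosing non-compliers and major deviators, and the ITT population keeps everyone. Because removal is discretionary, it may also differ between sites.

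At stake is the completeness of the co-primary data, some dilution of the treatment difference, and a possible shift in either direction if removals are unequal between arms.

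**Working it through.** **1. How early a substituted score can be.** The visit windows are Visit 2 Day 5–9, Visit 3 Day 12–16 and Visit 4 Day 26–30.

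- Visit 3 score carried: 26 − 16 = 10 to 30 − 12 = 18 days early.
- Visit 2 score carried: 26 − 9 = 17 to 30 − 5 = 25 days early.

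An exit assessment falls wherever the exit falls.

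**2. Reproducing the planned power.** Section 10.2 gives 40% versus 12%, 50 per arm, two-sided 5% Z-test, 100% correlation between the endpoints (so one endpoint's power is the joint power) and 89% power. With pooled variance under the null,

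power = Φ{ [ (p1 − p2) − 1.96·√(2·p̄(1 − p̄)/n) ] / √( [p1(1 − p1) + p2(1 − p2)]/n ) }.

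For n = 50 and p̄ = 0.26: (0.28 − 1.96 × 0.0877)/0.0831 = 1.30, so power is 90.3%. Other versions give 92.0% (unpooled), 87.2% (Fisher exact) and 85.5% (continuity-corrected). The stated 89% lies within this range, and nothing in the sample size is wrong on this point.

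**3. Full follow-up.** The ITT population is all randomized patients, up to 60 per arm. For n = 60: (0.28 − 1.96 × 0.0801)/0.0759 = 1.62, so power is 94.8%.

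**4. Equal removal in both arms.** Assumptions: a share r of each arm is removed; those removed would have had their arm's planning rate at Day 28; their carried success rate is f times that rate. Each arm's rate becomes p(1 − r + r·f).

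| Removed per arm | f | Test | Vehicle | Difference | Power |
|---|---|---|---|---|---|
| 0 | – | 40.0% | 12.0% | 28.0 points | 94.8% |
| 3 (5%) | 0.5 | 39.0% | 11.7% | 27.3 | 94.0% |
| 6 (10%) | 0 | 36.0% | 10.8% | 25.2 | 91.3% |
| 10 (16.7%) | 0.5 | 36.7% | 11.0% | 25.7 | 92.0% |
| 10 (16.7%) | 0 | 33.3% | 10.0% | 23.3 | 88.3% |

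Ten per arm is the whole allowance between 60 enrolled and 50 evaluable in section 10.2.

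**5. Unequal removal, as outer cases.** Ten removed from one arm only, f from 0 to 0.5:

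- Test only: difference 21.3 to 24.7 points, power 80.5% to 89.3%.
- Vehicle only: difference 30.0 to 29.0 points, power 97.5% to 96.3%.

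The shares removed and the values of f are assumptions; the protocol gives neither.

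**The case against.** The strongest reply is that the protocol misstates nothing. Both removal rules are permissive, and the definition of dosing non-compliance in 9.4.5 does not itself trigger removal. Section 9.3.5 already asks for every effort to complete Visit 4, which is defined as Day 28 ± 2. On that reading the score is sought and only a timing ambiguity remains. This softens the point but does not remove it: 9.3.5 sets no date, 9.6.7 uses the same procedures at discontinuation, and 11.2.4 lets an exit assessment stand as Visit 4.

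A second reply is that dilution costs some power but does not raise the false-positive risk. For equal removal with lower early success, that stands.

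Three stronger readings are tempting, and the documents do not support them.

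- A reader might infer that a handful of removals would bring power below plan. That needs removals in the Test arm alone, each with a 40% to 100% chance of Day 28 success. Site staff are blinded (9.4.4), and patients who lapsed and may have stopped drug would plausibly do worse than the arm average. At an assumed 20% chance, 6 Test-only removals give a Test rate of 0.40 − 0.20 × 6/60 = 38.0% and power of 91.8%.
- A reader might infer from the mention of significant deviators in 9.3.5 that LOCF overrides an observed Day 28 score. That is strained: LOCF fills a missing value, and the sentence mainly keeps such patients in the ITT population.
- A reader might infer that a scoring rule for users of prohibited treatment is missing. Section 10.1 leaves missing and spurious data to the SAP, so its absence here is no gap.

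**Conclusion.** The point holds as a modest design improvement, not as an error in the statistics. The protocol permits removal from the study for conduct reasons, fixes no Day 28 assessment afterwards, and carries an earlier score into the primary analysis. This is a rule of conduct, so the protocol is the place to settle it.

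The frequency is unknown and the effect probably small. Under equal removal, with all removed patients carried as failures and arm-average Day 28 rates otherwise, power stays above the planned 89% at 6 per arm and falls just below it only at 10 per arm. Unequal removal could shift the difference either way, but nothing in the documents suggests which way or how far. If sites read 9.3.5 as a recall at Day 28, the loss is smaller still.

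**What to change.** - **Sections 9.3.3 and 9.3.4:** for non-compliance or a restriction breach, say that study drug may be stopped and the deviation is recorded, but that unless consent is withdrawn the patient attends the remaining scheduled visits, including Visit 4 at Day 28 ± 2.
- **Sections 9.3.5 and 11.2.4:** record any exit assessment with its actual date as an early-termination visit. The Visit 4 form then holds only Day 28 ± 2 scores, and LOCF applies only where no such score exists.
- **Unchanged:** the rules for safety, worsening, possible HPA axis suppression and pregnancy. How users of prohibited treatment are scored stays with the SAP. If they are scored as failures, the gain for the co-primaries is confined to dosing lapses and other breaches.

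The cost is a few sentences, one early-termination page in the case report form, and a few off-drug visits. Those visits are already on the schedule.

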### 9.3.5 Early Terminations

If a patient terminates from the study early, all efforts will be made to complete Visit 4 study procedures. In case of early termination the Investigator shall fully document the reason for early termination.

Patients who discontinue early or who significantly deviate from the protocol will be included in the intent-to-treat (ITT) population with LOCF.

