### **9.3.3      Restrictions during the Study**

The following concomitant medications will not be allowed while enrolled in the study:

- Any prescription or OTC topical, systemic, phototherapy or biological medications or treatments for psoriasis.
- Application of any emollient on the treatment area.
- Any non-steroidal immunosuppressants (by any route of administration).
- Use of non-sedating anti-histamines.
  - The use of sedating anti-histamines, such as diphenhydramine, may be acceptable on condition the patient has been on a stable dose for at least 14 days before enrollment and will remain on a stable dose throughout the study.
- Any oral, topical or injectable steroid drug use (with the exception of HRT and contraceptives).
  - Female patients using hormonal contraceptives or HRT should have been on the same product/dosing regimen for at least 4 weeks before and should not change this during the study.
- New regimens of inhaled corticosteroids.
  - Inhaled or intranasal corticosteroids are permissible, provided that the patient has been on a stable regimen for at least 2 weeks before the first dose of study drug and will continue during the study.
- Any other treatments, prescription or over-the-counter products for the treatment of any other dermatological condition including; topical corticosteroids, antibacterial, medicated and/or astringent washes, soaps, pads or moisturizers during the study.
- Use of high strength (20% or above) alpha-hydroxy acid or any kind of peel or other procedures on the treatment areas (laser hair removal) during the study.

Patients will be advised to avoid environmental conditions that may exacerbate their disease state. Patients will be advised to avoid exposure to sunlight of a duration that would require application of sunscreen.

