#### **10.3 Study Populations**

##### **10.3.1 Intent-to-Treat (ITT) Population**

The ITT population will include:

- All randomized subjects.

Patients discontinued early for any reason will be included in the ITT with their Last Observation Carried Forward (LOCF).

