### **10.3.2 Per-Protocol (PP) Population**

The PP population is a sub-population of the ITT population and will include:

- Patients who met all inclusion and exclusion criteria and were randomized according to the randomized treatment assignment.
- Patients who applied at least one dose AND had at least one post-baseline evaluation.
- Patients who were compliant with the dosage regimens following randomization.
- Patients who had no major protocol deviations.

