### **Definitions:**

1. Treatment Success: To be considered a Treatment Success the patient's TLSS value at Day  $28 \pm 2$  must be 0 if their baseline TLSS value is 2 and must be 0 or 1 if their baseline TLSS value is  $> 2$  for each of the individual signs and symptoms
2. Treatment Failure: A patient will be considered a Treatment Failure if:
  - a. the patient's TLSS value is  $> 0$  if their baseline TLSS value is 2 or  $> 1$  if their baseline IGA score is  $> 2$  for any of the individual signs and symptoms
  - b. the patient was considered to have an insufficient therapeutic response
3. Clinical Success: To be considered a Clinical Success the patient must have at least a 2-grade improvement from their baseline IGA score. That is, an IGA score of 0 at Day  $28 \pm 2$  if their baseline IGA score is 2 or an IGA score of 0 or 1 at Day  $28 \pm 2$  if their baseline IGA score is 3
4. Clinical Failure: A patient will be considered a Clinical Failure if:
  - a. the patient's IGA score is  $> 0$  if the baseline IGA score is 2 or  $> 1$  if the baseline IGA score is 3
  - b. the patient was considered to have an insufficient therapeutic response

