### **10.6 Primary Efficacy Analyses**

The Test treatment will be compared with Placebo for each primary endpoint at the 5% significance level ( $p < 0.05$ ; two-sided, Cochran-Mantel-Haenszel exact test) in the ITT population using last observation carried forward (LOCF). Superiority of Test over Placebo will be demonstrated if both dichotomous endpoints show statistical significance at the 5% significance level.

For sensitivity testing, the primary analysis will also be performed using the PP population.

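### Scores reached on a prohibited psoriasis treatment can count as study-drug success in the primary ITT analysis, because no stated rule classifies them

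*Protocol*

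**What the plan says.** All of this is in the protocol.

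- **Restrictions (9.3.3).** The treatments not allowed during the study include: "Any prescription or OTC topical, systemic, phototherapy or biological medications or treatments for psoriasis". The stated consequence is discretionary: "Any patient who violates any of the listed restrictions may be dropped from continued participation in the study by the Investigator".
- **Early terminations (9.3.5).** "Patients who discontinue early or who significantly deviate from the protocol will be included in the intent-to-treat (ITT) population with LOCF". The same section asks that Visit 4 procedures be completed where possible when a patient stops early.
- **ITT (10.3.1).** The population is: "All randomized subjects". LOCF applies to early discontinuation for any reason.
- **Endpoint definitions (10.5).** Clinical Success depends only on baseline and Day 28 IGA, and Treatment Success only on baseline and Day 28 TLSS. Failure is the complementary score rule, criterion (a), or criterion (b): "the patient was considered to have an insufficient therapeutic response". Criterion (b) has no threshold, assessor or timing.
- **Analysis (10.6).** The ITT with LOCF is primary, and both endpoints must reach significance. In addition: "For sensitivity testing, the primary analysis will also be performed using the PP population". The PP set (10.3.2) is limited to: "Patients who had no major protocol deviations", among other conditions. Major is not defined, and prohibited medication is not named.

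**The concern.** Read together, these sections leave a route by which another treatment's effect is credited to the study product. A patient who uses a banned topical steroid or phototherapy may stay in the study, be scored at Day 28 and meet both success definitions. A patient who stops early may complete Visit 4 procedures after starting the other treatment, and that score can then be the last observation. Criterion (b) is unlikely to catch either patient, because someone who looks clear is the least likely to be judged an insufficient responder.

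At stake are the meaning of both co-primary endpoints and the size of the treatment difference. Crediting such successes raises the vehicle rate from a low base of 12%, while the Test rate has much less room to move.

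**Working it through.** **Inputs from the protocol (10.2, 10.6).** Success 40% on Test and 12% on vehicle; 50 evaluable patients per arm, up to 60 enrolled; two-sided 5%; stated power 89%. The two endpoints are taken as 100% correlated, so joint power equals single-endpoint power.

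**Reproducing the stated power.** For the pooled Z-test, power = Φ{[Δ − 1.96·√(2p̄(1−p̄)/n)] / √[(p₁q₁ + p₂q₂)/n]}. With Δ = 0.28, p̄ = 0.26 and n = 50, this is Φ{[0.28 − 1.96 × 0.0877] / 0.0831} = Φ(1.30) = 90.3%, close to the stated 89%. The two-sided Fisher exact test, by full enumeration, gives 87.2% at 50 per arm and 92.6% at 60. Fisher without strata stands in below for the planned exact Cochran-Mantel-Haenszel test.

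**Inputs that are assumptions.** qV and qT are the proportions using a prohibited psoriasis treatment on vehicle and Test; r is the success rate after such use. The protocol gives none of them. Its nearest figure for r is the 31-53% success with the 0.25% spray in the two earlier trials (10.2).

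**Formulas.**
- Scores as observed: Test = (1 − qT)·0.40 + qT·r; vehicle = (1 − qV)·0.12 + qV·r.
- Users counted as failures: Test = (1 − qT)·0.40; vehicle = (1 − qV)·0.12.

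**Results (Fisher exact power, 50 / 60 per arm).**

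| qV, qT, r | Test v vehicle, as observed | Power as observed | Power, users as failures |
|---|---|---|---|
| none | 40% v 12% | 87% / 93% | 87% / 93% |
| 2%, 1%, 40% | 40% v 12.6% | 85% / 91% | 87% / 93% |
| 5%, 2%, 40% | 40% v 13.4% | 82% / 89% | 87% / 93% |
| 15%, 5%, 60% | 41% v 19.2% | 60% / 68% | 89% / 94% |
| 10%, 10%, 50% | 41% v 15.8% | 76% / 83% | 82% / 88% |

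Worked example for the fourth row: vehicle = 0.85 × 0.12 + 0.15 × 0.60 = 0.192; Test = 0.95 × 0.40 + 0.05 × 0.60 = 0.410. The difference falls from 28 to 21.8 points.

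**Direction.** Scoring as observed changes the difference by qT(r − 0.40) − qV(r − 0.12).
- With equal use q, this is −0.28q, so the contrast shrinks whatever r is.
- With r between 12% and 40%, it cannot be positive.
- Above 40%, the contrast widens only if qT/qV exceeds (r − 0.12)/(r − 0.40): 0.38/0.10 = 3.8 at r = 50%, 0.48/0.20 = 2.4 at 60%, 0.58/0.30 = 1.9 at 70%.

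An inflating case exists. With 10% use on Test only and r = 70%, the rates are 43% v 12%, a 31-point difference (pooled Z power 94.6%). Counting users as failures gives 36% v 12% (81.2%).

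**The case against.** The strongest objection is that the protocol never says a score taken after prohibited treatment is the value analysed. Nothing is missing for a deviator who attends Day 28, so LOCF has work to do there only if the later score is set aside and an earlier one carried forward. On that reading the problem largely disappears. The point stands as an ambiguity: a reader might infer that the protocol positively counts such clearance as success, and the text does not go that far. It does not state the protective reading either.

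Section 10.1 leaves missing, unused and spurious data to the SAP, which is not at hand and may settle the question. But a recorded Day 28 score is not missing. The retention of deviators and the success definitions are fixed in the protocol, so the classification belongs beside them.

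There are existing protections. Medication use is asked about at each visit, criterion (b) could catch some patients, and the PP analysis should remove major deviators. These help only in part. Criterion (b) is undefined, and the PP analysis is a sensitivity analysis that excludes such patients instead of classifying them.

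On size, every use rate is assumed. The 60% floor combines the worst value of all three assumptions with 50 per arm, whereas the ITT is all randomised patients, up to 60 per arm. The 12% base comes from earlier vehicle arms, and the protocol does not say whether those were free of such use. All of this stands and limits what can be claimed. Dilution works against the sponsor; it does not inflate type I error.

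**Conclusion.** The point holds as a gap in endpoint classification. A score obtained after a prohibited psoriasis treatment can count as study-drug success in the primary analysis, and sections 9.3.3, 9.3.5, 10.3.1 and 10.5 do not settle whether it does.

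A reader might infer that the contrast is necessarily diluted, or that power will fall to 60%. The documents support neither. Dilution follows at equal use, or at higher use on vehicle, provided success after use exceeds 12%. It reverses only if success after use exceeds 40% and use on Test is well above use on vehicle. The loss of power ranges from about 1-2 points at 1-2% use to 5-28 points at 50 per arm under the assumed 5-15% and 2-5% use (87% to 82-60%; at 60 per arm, 93% to 89-68%). These are single-endpoint figures and rely on the plan's assumption of full correlation between the two endpoints.

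**What to change.** Add to both failure definitions in section 10.5, and mirror in the SAP: a patient who used a prohibited treatment active against psoriasis before the Day 28 assessment, as judged blind from the concomitant medication record before database lock, is a failure at Day 28 whatever the score. Keep the observed/LOCF result as a sensitivity analysis, and state which score LOCF carries for a deviator who attends Day 28. This concerns classification only and changes nothing in patient management.

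A parallel clause for stopping because of lack of efficacy or worsening would add little, since such carried scores already fail criterion (a).

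The cost is wording, because medication use is already recorded at each visit. There are two statistical downsides. A few patients whose banned use did not affect the outcome become failures. The rule also does not always restore baseline power: with equal 10% use, power at 50 per arm is about 82% against 87% with no use, though still above the 76% from scoring as observed at 50% success. If use were mainly on Test, the rule would lower power, but it would also remove successes that the study product may not have earned.
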